COVID-19	coronavirus disease 2019
D	day
eCRF	electronic case report form
ECLIA	electrochemiluminescence immunoassay
ELISA	enzyme linked immunosorbent assay
FAS	full analysis set
GBS	Guillain-Barré Syndrome
GM	geometric mean
GM-CSF	granulocyte-macrophage-colony-stimulating factor
GMC	geometric mean concentration
GMT	geometric mean titer
ICD-10	10th revision of the International Statistical Classification of Diseases and Related Health Problems
IFN	interferon
IL	interleukin
IRT	interactive response system
LLOQ	lower limit of quantification
LNP	lipid nanoparticle
MAAE	medically attended adverse event
MD	missing data
MedDRA	Medical Dictionary for Regulatory Activities
MERS-CoV	Middle East Respiratory Syndrome coronavirus
mRNA	messenger ribonucleic acid
NA	not applicable

NAAT	nucleic acid amplification test
NOCMC	new-onset chronic medical condition
PBMC	peripheral blood mononuclear cell
PCA	principal component analysis
PPAS	per-protocol analysis set
PPAS-IAS	per-protocol analysis set for immunogenicity
PPAS-AIT	per-protocol analysis set for AIT subset
PT	preferred term
PV	Pharmacovigilance
Q1; Q2; Q3	first quartile; second quartile (median); third quartile
RCDC	reverse cumulative distribution curve
RMO	Responsible Medical Officer
RNA	ribonucleic acid
S	spike
SAE	serious adverse event
SafAS	safety analysis set
SARS-CoV-2	severe acute respiratory syndrome coronavirus 2
SAP	statistical analysis plan
SMT	Safety Management Team
SOC	system organ class (primary)
Th	T helper cell
THGM	granulocyte-macrophage-colony-stimulating factor-producing T helper
TLF	table(s), listing(s), and figure(s)
TNF	tumor necrosis factor
ULOQ	upper limit of quantification
US	United States
V	visit
VAC	vaccination
VE	vaccine efficacy

1 Introduction

Severe acute respiratory syndrome coronavirus 2 (SARS-CoV-2) is a novel coronavirus that emerged in the human population and has led to a pandemic of acute respiratory disease named coronavirus disease 2019 (COVID-19). Coronaviruses are a family of large, enveloped, positive-sense, single-stranded ribonucleic acid (RNA) viruses that infect a wide variety of mammalian and avian species. In the last 20 years, 3 zoonotic coronaviruses are known to have crossed species to cause SARS in humans which include SARS-CoV, SARS-CoV-2, and the more distantly related Middle East Respiratory Syndrome coronavirus (MERS-CoV) (1). Coronavirus entry into the host cells is mediated by the transmembrane spike (S) glycoprotein which permits both the binding to the host cell receptor (via the S1 subunit) and the fusion of viral and cellular membranes (via the S2 subunit). Recent work has shown that the SARS-CoV-2 receptor binding gene region is similar to SARS-CoV and uses the same receptor, angiotensin-converting enzyme 2, on the human cell surface (2).

To address the urgent medical need caused by the COVID-19 outbreak, Sanofi Pasteur is developing a SARS-CoV-2 messenger ribonucleic acid (mRNA) vaccine consisting of an mRNA encoding the entire sequence for the prefusion stabilized form of the SARS-CoV-2 S protein with 2 sets of mutations, first in the S2 portion of the S protein that locks the expressed S protein in the prefusion conformation, and second at the S1/S2 cleavage site which prevents the cleavage of the expressed protein into the S1 and S2 subunits. The mRNA vaccine is complexed with a novel lipid nanoparticle (LNP) vehicle [REDACTED]. Prior to this study, neither the LNP nor the mRNA targeted in this study had been administered to humans before. However, studies with the SARS-CoV-2 mRNA vaccine in rabbits [REDACTED], mice [REDACTED], hamsters [REDACTED], and non-human primates (NHP; [REDACTED]) supported the safety, immunogenicity, and protective efficacy of this vaccine (for more details see the Investigator's Brochure). The investigational vaccine candidate uses a technology platform developed with an ongoing collaboration between Translate Bio and Sanofi Pasteur and was manufactured by Translate Bio.

VAW00001 is a first-in-human Phase I/II, multi-center study comprised of 2 sequential cohorts: a lead-in open-label Sentinel Cohort, followed by a randomized, modified double-blind, dose-ranging, placebo-controlled Full Enrollment Cohort, to evaluate the safety and immunogenicity of the SARS-CoV-2 mRNA vaccine in healthy adult participants (18 years of age and older) in the United States (US), Honduras, Brazil, and Australia. In its original design, the study was to evaluate 3 different dose-levels [REDACTED] of the candidate mRNA vaccine with the goal of selecting the optimal dose and schedule to proceed to a Phase III study.

[REDACTED] and the Sponsor introduced 4 changes through a protocol amendment:

- 1) Add an "ultra-low-dose" arm of [REDACTED] µg [REDACTED] to evaluate [REDACTED]

██████████ a lower dose-level range (ie, ultra-low- [████ μg], low- [████ μg], and medium- [████ μg] dose-levels).

- 2) Increase the number of Sentinel Cohort participants from 5 to 10 in the dose-level groups that had yet to start enrollment (ie, ultra-low- and medium-dose-levels).
- 3) Include an option to add an expansion of the open-label Sentinel Cohort for the █████ μg dose-level to better understand the reactogenicity at this dose-level in a larger group of participants prior to escalation to the █████ μg dose. This possibility to expand the number of Sentinel Cohort participants was also extended to the ultra-low- and medium-dose groups, if needed.
- 4) Decrease the number of placebo recipients in the Full Enrollment Cohort.

After the planned preliminary interim of the Sentinel Cohort participants, a decision to discontinue the development of the mRNA COVID-19 vaccine was made. On September 27, 2021, all Investigators were informed to terminate further vaccinations and enrollment. All enrolled participants were to be unblinded to allow them to make their decision to receive an authorized COVID-19 vaccine. All clinical sites were to contact participants to inform them of the discontinuation of further study vaccinations, told what intervention they received and invited to come in for an unscheduled visit for counseling to answer any questions about the study, to discuss available options for receipt of an approved /authorized COVID vaccination, and were requested to provide unscheduled blood draw for serological assessment (UBXX). Participants were informed that additional D22 or D36 blood draws for serological assessment would be appreciated but are not mandatory. No protocol defined schedule visits or blood draws at timepoints later than D36 were required. Monitoring for SAEs, AESIs, medically attended AEs, and pregnancy and collection of influenza and COVID-19 vaccines were continued with safety calls. On March 15, 2022, after concurrence from regulatory authorities, Investigators were notified of the decision to end the study at the 6-month safety follow-up instead of 12-month follow-up.

This version 5.0 of SAP is updated for the final unblinded analysis. The sections of Trial Objectives and Trial Design and Plan are kept the same with the final protocol, but modifications are made in Section 4 and Section 5 for endpoint derivation, statistical methods, and populations used in analyses, to reflect the changes needed for the final analyses.

2 Trial Objectives

2.1 Primary Objectives

Safety

To describe the safety profile of all participants in each age group and each study intervention group up to 12 months post-last dose.

Immunogenicity

To describe the neutralizing antibody profile at D01, D22, and D36 of each study intervention group.

2.2 Secondary Objectives

Immunogenicity

- 1) To describe binding antibody profile at D01, D22, D36, D91 (Cohort 1) or D112 (Sentinel Cohort and Cohort 2), D181 (Cohort 1) or D202 (Sentinel Cohort and Cohort 2), and D366 (Cohort 1) or D387 (Sentinel Cohort and Cohort 2) of each study intervention group.
- 2) To describe the neutralizing antibody profile at D91 (Cohort 1) or D112 (Sentinel Cohort and Cohort 2), D181 (Cohort 1) or D202 (Sentinel Cohort and Cohort 2), and D366 (Cohort 1) or D387 (Sentinel Cohort and Cohort 2) of each study intervention group.

Efficacy

- 1) To describe the occurrence of virologically-confirmed COVID-19-like illness and serologically confirmed SARS-CoV-2 infection.
- 2) To evaluate the correlation/association between antibody responses to SARS-CoV-2 mRNA vaccine and the risk of virologically-confirmed COVID-19-like illness and/or serologically confirmed SARS-CoV-2 infection.

2.3 Exploratory Objectives

Immunogenicity

- 1) To assess the T-cell cytokine profile at D01, D22 and D36 in the Additional Immunological Tests (AIT) subset.
- 2) To further assess the cellular immune response at D01, D22, D36, and D112 in the AIT subset.
- 3) To describe the ratio between neutralizing antibodies and binding antibodies.
- 4) To describe the neutralizing antibody response to emergent SARS-CoV-2 variant strains at each pre-defined time point of each study intervention group.

Other

To evaluate other emerging biomarkers for immune profiling (further characterization of humoral and/or cellular responses which may include cell profiling), as effect modifiers (may include viral characterization) or as correlates of risk/protection.

3 Description of the Overall Trial Design and Plan

3.1 Trial Design

This is a Phase I/II, first-in-human, multi-center, safety and immunogenicity study comprised of 2 sequential cohorts: a lead-in, open-label, dose escalation Sentinel Cohort (initial target of 25 participants) with Complete Sentinel Early Safety Data Reviews (CS-ESDRs), followed by a

randomized, modified double-blind, dose-ranging, placebo-controlled Full Enrollment Cohort (initial target of 308 participants, but actual number could be lower as it will be determined by dose-levels progressing after CS-ESDR), to evaluate the safety and immunogenicity of the SARS-CoV-2 mRNA vaccine in healthy adult participants (18 years of age and older) in the US and Honduras.

Participants in the Initial Sentinel Cohort were 18-49 years of age at enrollment and were assigned to receive 2 injections of one of the 3 dose-levels (ultra-low-dose [■] µg], low-dose [■] µg] and medium-dose [■] µg]) of the study vaccine, 21 days apart, in a stepwise open-label manner. In case an alert threshold was met in a dose-level group in the Initial Sentinel Cohort, the corresponding dose-level group could be expanded to reach a total of approximately 25 participants as shown in Figure 1.5 of the protocol. Details of the planned safety parameters and alert thresholds to be examined for the Sentinel Cohort safety analysis are provided in Section 8.4.1 and Section 8.4.2 of the protocol. The Full Enrollment Cohort includes both Cohort 1 and Cohort 2. Participants in Cohort 1 of the Full Enrollment Cohort (hereafter referred to as Cohort 1) were to receive a single injection of study intervention while participants in Cohort 2 of the Full Enrollment Cohort (hereafter referred to as Cohort 2) were to receive 2 vaccinations (to be given 21 days apart), of one of the study interventions (ultra-low-dose [■] µg], low-dose [■] µg], medium-dose [■] µg], or placebo). Halting rules for the Entire Study are provided in Section 8.4.3 of the protocol.

The study targeted enrollment of approximately 333 participants 18 years of age and older, [REDACTED]. The actual number of participants enrolled depended on which dose-level groups were allowed to be evaluated in the Sentinel Cohort and the Full Enrollment Cohort. The number could have been higher if Expanded Sentinel Cohorts were exercised for all dose-levels, and if all dose-levels progress to the Full Enrollment Cohort (maximum number of study participants approximately 383); conversely, the number could have been lower if not all the dose-levels were evaluated in the Sentinel Cohort or/and not all the dose-levels progress to the Full Enrollment Cohort. A subset of up to 77 randomly selected participants in Cohort 2 was to be included in an AIT subset. Please refer to Table 4.2 and Table 4.3 of the protocol for the planned sample size in Sentinel Cohort and Full Enrollment Cohort.

Further details about the planned study procedures are given in Table 1.3 to Table 1.6 of the protocol.

It should be noted that throughout the study, the Sponsor's Safety Management Team (SMT) core members, consisting of Clinical Team Leader (Responsible Medical Officer [RMO]), Study Biostatistician, Pharmacovigilance Science Expert, and Global Safety Officer, continuously reviewed blinded safety data, except for the safety reviews for the Sentinel Cohort, during which unblinded safety data was reviewed. The blind was broken at the group level for the Sponsor at the time of each interim analysis. Further unblinding could have been performed if any of the halting rules were met (see Section 8.4.3 of the protocol) or if there was any safety concern.

Participants were followed over the duration of the study for development of symptoms of COVID-19-like illness. Participants received surveillance phone calls every 2 weeks (\pm 6 days starting after the D43 contact to approximately 6 months) or could have been contacted through alternative contact methods (text messages, email, and/or home visit) to enquire about the

development of symptoms of COVID-19-like illness and to remind the participants to contact study staff if they experienced symptoms of COVID-19-like illness. In addition, all participants had been instructed to contact the site if they experienced symptoms of a COVID-19-like illness at any time during the study. The reporting of events temporally associated with COVID-19-like illness are outlined in Table 1.6 of protocol.

Participants were free to receive an authorized/approved COVID-19 vaccine. If the participant received an authorized/approved COVID-19 vaccine, this information was collected and the participant's data up to the point of receipt of an authorized/approved COVID-19 vaccine was included in the analysis. Participants continued to be followed for the duration of the study as per scheduled visits and procedures. Participants were invited to a visit prior to receiving the vaccine and requested to provide a blood sample for immunological assessment. Participants were not to receive the second vaccination if they had received an authorized/approved COVID-19 vaccine between the first and second scheduled vaccination.

3.2 Trial Plan

The graphical design of VAW00001 study is as presented in Figure 1.1 to Figure 1.5 in the protocol.

4 Endpoints and Assessment Methods

4.1 Primary Endpoints and Assessment Methods

See Table 3.1 of the protocol for endpoints. For Assessment methods, see protocol Section 8.2.1.1 for primary immunogenicity; see protocol Section 8.3.4 and Section 8.4 for primary safety.

4.2 Secondary Endpoints and Assessment Methods

See Table 3.1 of the protocol for endpoints. For Assessment methods, see protocol Section 8.2.1.1 and Section 8.2.1.2 for secondary immunogenicity; see protocol Section 8.2.2 for secondary efficacy.

4.3 Exploratory Endpoints and Assessment Methods

See Table 3.1 of the protocol for endpoints. For exploratory immunogenicity assessment methods, see protocol Section 8.2.1.2.

4.4 Derived Endpoints: Calculation Methods

4.4.1 Safety

The main safety analysis will include all events or reactions with time of onset before the date of receiving a non-study authorized/approved COVID-19 vaccine and including only the corresponding safety data collected before the date of receiving a non-study authorized/approved COVID-19 vaccine. The endpoints derivations for safety analysis are detailed in the following sections. Conducting main analysis with data censored by the date of receiving a non-study authorized/approved COVID-19 vaccine will only be applied to some selected endpoints. Details on the conduct of the main safety analysis for those endpoints are provided in the following subsections. Other endpoints will be analyzed as usual. Events or reactions with time of onset on or after the date of receiving a non-study authorized/approved COVID-19 vaccine will be listed separately.

4.4.1.1 Solicited Reactions

4.4.1.1.1 Daily Intensity

All daily records for solicited reactions will be derived into daily intensity according to the following classification: None, Grade 1, Grade 2, Grade 3, or Missing.

For measurable injection site reactions:

- None: > 0 to < 25 mm
- Grade 1: ≥ 25 to ≤ 50 mm
- Grade 2: ≥ 51 to ≤ 100 mm
- Grade 3: > 100 mm

For Fever:

- None: $< 38.0^{\circ}\text{C}$ or $< 100.4^{\circ}\text{F}$
- Grade 1: $\geq 38.0^{\circ}\text{C}$ to $\leq 38.4^{\circ}\text{C}$ or $\geq 100.4^{\circ}\text{F}$ to $\leq 101.1^{\circ}\text{F}$
- Grade 2: $\geq 38.5^{\circ}\text{C}$ to $\leq 38.9^{\circ}\text{C}$ or $\geq 101.2^{\circ}\text{F}$ to $\leq 102.0^{\circ}\text{F}$
- Grade 3: $\geq 39.0^{\circ}\text{C}$ or $\geq 102.1^{\circ}\text{F}$

For the derivation of daily intensities, the following sequential steps will be applied:

- 1) Solicited reactions (except fever/pyrexia) with an Investigator presence recorded as “No” and with all daily records missing then all daily intensities will be derived as “None”.
- 2) For non-measurable solicited reactions, daily intensities will correspond to daily records reported in the clinical database. For measurable solicited reactions the daily measurements reported in the clinical database will be converted based upon the intensity scales defined in the protocol; this assumes a reaction that is too large to measure (non-measurable, “NM”) is Grade 3. Note: the intensity could be considered “None” (not a reaction) in the analysis

despite being considered a reaction by the Investigator (eg, swelling measurement > 0 mm but < 25 mm in adults).

Note: The maximum intensity on the ongoing period is derived from the record of the maximum intensity/measurement after the end of the solicited period following the rule described above.

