4.4.1.1.3 Presence

Presence is derived from the maximum overall intensity on the period considered:

- None: No presence
- Grade 1, Grade 2, or Grade 3: Presence
- Missing: Missing presence

Participants with at least one non-missing presence for a specific endpoint will be included in the analysis. Conversely, those without a non-missing presence will not be included in the analysis of the endpoint.

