5.3 Handling of Missing Data and Outliers

5.3.1 Safety

Generally, no replacement will be done. However, imputations may be done for a limited number of scenarios, some of which are described in this section.

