5.3.1.4 Intensity

For solicited reactions, missing intensities will be handled as described in [Section 4.4.1.1.1](#). For unsolicited non-serious AEs, missing intensities will remain missing and will not be imputed.

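### For non-measurable solicited reactions with no daily records, the SAP keeps an Investigator 'No' as a non-reaction but excludes an Investigator 'Yes', so each such 'Yes' lowers the any-grade rate

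*SAP*

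**What the plan says.** SAP 4.4.1.1.1 derives daily intensities in two ordered steps. Step 1 covers solicited reactions other than fever, "with an Investigator presence recorded as “No” and with all daily records missing then all daily intensities will be derived as “None". Step 2 handles everything else: "For non-measurable solicited reactions, daily intensities will correspond to daily records reported in the clinical database". Redness and swelling are graded from the recorded size.

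SAP 4.4.1.1.2 takes the maximum of the daily intensities. SAP 4.4.1.1.3 then states: "Presence is derived from the maximum overall intensity on the period considered". A maximum of None means no reaction, Grade 1 to 3 means a reaction, and Missing means missing presence. For the last group: "Conversely, those without a non-missing presence will not be included in the analysis of the endpoint".

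The missing-data section adds no rule. SAP 5.3.1.4 says "For solicited reactions, missing intensities will be handled as described in" SAP 4.4.1.1.1. SAP 5.3.1 opens with "Generally, no replacement will be done", while allowing imputation in a limited number of scenarios, only some of which it describes.

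**The concern.** The Investigator's presence field is used when it records no reaction and ignored when it records one. For pain, headache, malaise, myalgia, arthralgia and chills, a reaction can be known to have occurred without a size or a temperature. A 'Yes' on these is therefore enough to establish any-grade presence, even when the grade is unknown.

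Presence of solicited reactions up to 7 days after each injection is a primary safety endpoint (Protocol Table 3.1), and planned groups are small: 44 per vaccine group in the Full Enrollment Cohort (Protocol Table 4.3) and about 25 per expanded Sentinel dose group (Protocol Table 4.2). One or two records can move a rate by several points. SAP 5.7 also drops the complementary and sensitivity analyses of safety data, so no listed analysis would show the loss.

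The SAP resolves similar gaps differently elsewhere. An unsolicited AE counts as an event if it has a verbatim term and is not Grade 0 (SAP 4.4.1.2.1), and a missing intensity stays missing (SAP 5.3.1.4): event present, grade unknown. A missing immediate flag is taken as immediate (SAP 5.3.1.1), and missing causality as related (SAP 5.3.1.2).

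**Working it through.** The documents give no expected reaction rate and no rate of missing diaries, so there is no planned figure to reproduce. The check has two parts.

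**1. Trace the two answers, with all daily records missing (non-measurable reaction)**

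| Step | Investigator 'No' | Investigator 'Yes' |
|---|---|---|
| 4.4.1.1.1 | None on every day (step 1) | Missing on every day (step 2) |
| 4.4.1.1.2 | maximum = None | maximum = Missing |
| 4.4.1.1.3 | no presence | missing presence |
| Analysis | in denominator | in neither numerator nor denominator |

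Exclusion of the 'Yes' is a consequence of these rules; no single sentence states it.

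**2. Effect on the rate**

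- N = participants with daily records or a recorded Investigator answer; illustrated at 44 (Protocol Table 4.3) and 25 (Protocol Table 4.2)
- T = those with the reaction; assumed
- k = those among T with 'Yes' and no daily records; not in the documents, assumed 1, 2 or 4

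Rate under the SAP = (T-k)/(N-k). Rate with 'Yes' counted = T/N.

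Difference = [N(T-k) - T(N-k)] / [N(N-k)] = -k(N-T) / [N(N-k)]

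This is negative whenever k>0 and T<N, and zero if k=0. For N=44, T=22, k=2 it is -2×22/(44×42) = -44/1848 = -2.4 percentage points.

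| N | T | T/N | k=1 | k=2 | k=4 |
|---|---|---|---|---|---|
| 44 | 11 | 25.0% | 10/43 = 23.3% | 9/42 = 21.4% | 7/40 = 17.5% |
| 44 | 22 | 50.0% | 21/43 = 48.8% | 20/42 = 47.6% | 18/40 = 45.0% |
| 44 | 33 | 75.0% | 32/43 = 74.4% | 31/42 = 73.8% | 29/40 = 72.5% |
| 25 | 6 | 24.0% | 5/24 = 20.8% | 4/23 = 17.4% | 2/21 = 9.5% |

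The number of 'No' answers without daily records does not enter the formula. Keeping them is correct; only the loss of 'Yes' moves the rate.

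**Redness and swelling.** SAP 4.4.1.1.1 notes that intensity may be None "despite being considered a reaction by the Investigator (eg, swelling measurement > 0 mm but < 25 mm in adults"). Let q be the share of dropped 'Yes' records that would reach 25 mm, and R the graded reactions observed. Counting them properly gives (R+qk)/N against R/(N-k) under the SAP. The SAP rate is lower only if q > R/(N-k). With N-k=40, the break-even q is 10% for R=4, 25% for R=10 and 50% for R=20. The documents do not give q.

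**Fever.** It is outside step 1, so 'No' and 'Yes' without temperatures are both Missing. There is no asymmetry.

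**The case against.** The best defence is that such records should be rare. Under Protocol 8.4.5 the site interviews participants, clarifies incomplete diary entries, and enters information missing from the diary through the source document. Protocol 10.3.5 requires an intensity grade for each AE. A 'Yes' with no intensity on any day is thus a gap that sites are expected to close. This stands, and it limits the likely size. It does not say what the analysis does with a record that remains open.

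The two answers also differ in kind. 'No' settles every daily intensity, while 'Yes' settles none. The CRF may even skip the daily fields after 'No', though the documents do not show it. This justifies keeping the 'No' rule and leaving the grade of a 'Yes' missing. It does not justify losing presence, which the 'Yes' does settle for non-measurable reactions.

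The imputation list in SAP 5.3.1 is not exhaustive, so an unlisted rule could exist. But SAP 4.4.1.1.3 already assigns an outcome to Missing, so a programmer following the text would exclude the record.

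Finally, the consequences are modest. The clinical-reaction alert thresholds in Protocol 8.4.1 and 8.4.2 concern Grade 3, which a 'Yes' of unknown grade would not change. SAP version 5.0 serves a descriptive final analysis after development was stopped. Both points stand.

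A reader might go further and infer that all solicited-reaction rates are biased downward. The documents do not support that: k is unknown and may be zero, fever is exempt, and dropping a 'Yes' for redness or swelling below 25 mm would raise the rate.

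**Conclusion.** The point holds for the six non-measurable solicited reactions. Following the stated rules, an Investigator 'Yes' with no daily records is discarded while the corresponding 'No' is kept, and each discarded 'Yes' lowers the any-grade presence rate unless everyone reacted. In the illustrations at N=44, with k from 1 to 4 and true rates of 25% to 75%, the shift is 0.6 to 7.5 percentage points; at N=25 and T=6 it is 3.2 to 14.5 points.

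These sizes rest on assumed T and k, on planned rather than achieved group sizes, and on taking an Investigator 'Yes' as a true reaction. They show sensitivity and do not estimate a bias that has occurred. It would be wrong to read this as a demonstrated downward bias, or as one covering fever, redness and swelling. Grade-specific rates depend on the unknown grades of the dropped records. The gap should be closed because the endpoint is primary and the change is small.

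**What to change.** Add to SAP 4.4.1.1.1 and 4.4.1.1.3: for non-measurable solicited reactions, Investigator presence 'Yes' with all daily records missing gives presence = Yes and maximum intensity = Missing, and the participant stays in numerator and denominator.

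For redness and swelling, keep the 'No' rule and report 'Yes' without a size as a separate count per group. Do not set 'No' to Missing for the sake of symmetry: a 'No' needs no size, and valid non-reactors would be lost. With 24 participants, 4 measured reactions and 20 'No' with blank days, the rate would go from 4/24 = 16.7% to 4/4 = 100%.

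The cost is one sentence in the SAP, one derivation line and one count per group, with no new data. Some any-grade rates may come out slightly higher; Grade 3 counts do not change.
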